We will power the study to detect a 250mL difference in calculated intra-operative blood loss between groups. This effect size has been used in the total hip literature, and it is considered to be a clinically significant difference in blood loss¹⁵. Our analysis shows that 12 patients are required in each arm of the study (24 patients total) to achieve 81% power with an independent-sample t-test and statistical significance set to alpha equal to 0.05. Expecting that 10-25% of patients will be excluded, we will aim to enroll a total of 30 patients in this study.

Patients aged 18 or younger will be screened for study eligibility

3. Interventions or Observations – what data are going to be collected and from what source?

Only anesthesiologists agreeing to participate in the study will be paired with the study surgeons. Anesthesia will be conducted in a standardized fashion. The anesthesiologist will perform a neuraxial block (epidural, spinal, combined-spinal epidural) as well as administer general anesthesia. A neuraxial block will be placed using bupivicaine. A balanced general anesthetic utilizing a combination of either isoflurane, sevoflurane with or without nitrous oxide, vecuronium, midazalam and either fentanyl, morphine or dilaudid as the narcotic will be used at the discretion of the anesthesiologist. If a combined-spinal epidural is unsuccessful and an epidural and/or spinal are successfully obtained, the patient will still be included in the study. Patients not receiving neuraxial anesthesia will be excluded from the study. Arterial and venous access will be obtained in the usual sterile manner for monitoring.

The blood pressure target will be 20-25% below baseline, which will be achieved primarily with the combination of the general anesthesia and the neuraxial anesthesia. For blood pressure above this range, the epidural will be dosed with a short-acting local anesthetic, and/or the depth of the general anesthetic and will be titrated as per the anesthesiologist's judgment. For hypotension below this range, intravenous pressors, crystalloid, colloid or blood will be given. The technique of induced hypotension will not be utilized during these cases. Additional maintenance IV fluids or colloid will be given to maintain urine output of at least 0.5-1ml/kg/hr. Toradol and IV acetaminophen may be given towards the end of the case per the anesthesiologist's discretion.

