Attending surgeons, orthopedic surgery residents, physician assistants and research assistants involved with this study will assist in data collection. For each patient, we will collect demographic data, pre-operative CBC data, intra-operative cell saver auto-transfusion volumes, post-operative number of packed red blood cell units transfused, post-operative CBC data, post-operative drain outputs, and post-operative complications. This information will be gathered from the peri-operative medical records and electronic medical records.

A sticker will be place on the front of each participating patient's chart identifying him or her as a study patient. Their enrollment will also be communicated in the clinician rounding notes for each patient. Drains will be labeled for each study participant as well, and nurses will record the drain outputs per their floor protocol.

Data recorded from the electronic medical record will include:

- Date of surgery
- Patient age at the time of surgery
- Patient sex
- Patient height (cm) and weight (kg) at time of admission
- Preoperative CBC data and coagulation study data

- Postoperative hemoglobin on all inpatient days postoperatively (g/dL)
- Transfusion requirement during inpatient stay (units required)
- Transfusion reaction
- Total 24-hour drain output
- Postoperative day and time of discharge
- Chart review of progress notes for evidence of clinically significant VTE
- Chart review of progress notes for evidence of reoperation, hematoma, seroma, or postoperative infection

Data recorded from the operating room record will include:

- Anesthetic used (e.g., spinal/epidural, general, etc.)
- Operative times (minutes)
- Intra-operative transfusion requirements (units of blood)
- Use of cell saver intraoperatively (auto-transfusion volume, mL)
- Intra-operative complications

Data recorded from outpatient postoperative office records will include:

- Chart review of progress notes for evidence of clinically significant VTE through six weeks post-operatively
- Chart review of progress notes for evidence of re-operation, hematoma, seroma, or postoperative infection through six weeks post-operatively

Patients will be randomized to either the intervention or control group, as per randomization protocol described elsewhere in the proposal. For patients who are randomized to the control group, study data will be collected in the same manner as for the intervention group.

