Secondary outcomes of interest: Postoperative transfusion requirements (allogeneic blood transfusion and intraoperative cell saver utilization), post-operative blood loss, length of stay, and post-operative complications.

Calculated total blood loss will be determined from the difference between the preoperative hemoglobin and the postoperative hemoglobin (or the lowest postoperative hemoglobin during the hospital stay prior to transfusion). Based on hemoglobin balance, the estimated blood loss will be calculated according to the formula by Nadler et al.¹⁷:

```
Estimated Blood Volume (EBV) = (k_1 \text{ x Height}^3 \text{ (m)}) + (k_2 \text{ x Weight (kg)}) + k_3
For men, k_1 = 0.3669, k_2 = 0.03219, and k_3 = 0.6041
For women, k_1 = 0.3561, k_2 = 0.03308, and k_3 = 0.1833
```

Multiplying the EBV by the hematocrit (Hct) gives the red blood cell (RBC) volume. As such, a change in the RBC volume can be calculated from a change in the Hct level^{23,24}:

```
Total RBC volume loss = EBV x (Hct Preop – Hct Postop)
```

Transfusions (mean volume per unit at HSS, 250 mL) can be taken into account by calculating the total blood loss¹⁶:

Total blood loss (L) = Total RBC volume loss + (No. of Units Transfused x 0.25) / (Hct Preop – Hct Postop) / 2)

The rate of perioperative blood transfusions, both intraoperative and postoperative, will be documented for analysis.

The criteria for transfusion of blood products will be a hemoglobin level of < 7.0 g/dL or a hemoglobin level of < 10.0 g/dL with clinical signs of symptomatic anemia (e.g., unexplained tachycardia, hypotension unresponsive to fluids or vasopressors, change in mental status, low

urine ouput, and shortness of breath). Blood will be administered 1 unit at a time, and the presence of symptoms or signs will be reassessed after each unit. This algorithm may be altered by the treating physician (e.g., PACU attending, surgeon, or the OR anesthesiologist), however all decisions will be supported by reasonable documentation. Drains will be removed on POD 2 unless specified by the attending surgeon. Of note, the chart of the patient will clearly indicate him/her as a study patient.

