The primary outcome of interest (calculated total blood loss) will be presented as a mean +/-standard deviation and compared between the EACA and placebo groups with a two-sample t-test. Multivariable linear regression models will also be used to adjust for any potential confounding due to total blood loss volume between arms after adjustment for age, sex, BMI, and anesthesia type. To adjust for any patients lost due to early withdrawal, we will increase our sample size by 3 patients in each group for a total sample size of 30 patients.

Calculated total blood loss will be determined from the difference between the preoperative hemoglobin and the postoperative hemoglobin (or the lowest postoperative hemoglobin during the hospital stay prior to transfusion). Based on hemoglobin balance, the estimated blood loss will be calculated according to the formula by Nadler et al.¹⁷:

```
Estimated Blood Volume (EBV) = (k_1 \text{ x Height}^3 \text{ (m)}) + (k_2 \text{ x Weight (kg)}) + k_3
For men, k_1 = 0.3669, k_2 = 0.03219, and k_3 = 0.6041
For women, k_1 = 0.3561, k_2 = 0.03308, and k_3 = 0.1833
```

Multiplying the EBV by the hematocrit (Hct) gives the red blood cell (RBC) volume. As such, a change in the RBC volume can be calculated from a change in the Hct level^{23,24}:

```
Total RBC volume loss = EBV \times (Hct Preop - Hct Postop)
```

Transfusions (mean volume per unit at HSS, 250 mL) can be taken into account by calculating the total blood loss¹⁶:

Total blood loss (L) = Total RBC volume loss + (No. of Units Transfused x 0.25) / (Hct Preop – Hct Postop) / 2)

All continuous secondary outcomes such as postoperative allogeneic blood transfusion requirement, intraoperative cell saver utilization, and length of hospital stay, will be analyzed in the same manner as the primary outcome.

Complications will be reported as incidence rates with 95% confidence intervals.

All hypotheses will be evaluated with two-sided tests with statistical significance set at $\alpha = 0.05$.

Bibliography

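### The only formula for the primary outcome does not parse, and every one-bracket repair gives untransfused patients a red-cell volume instead of a blood loss

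*Combined protocol and SAP*

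**What the plan says.** The combined protocol and SAP derives the primary outcome twice in the same words, once under Outcome Measures and once under section D, Data Analysis. Blood volume (EBV) comes from height and weight. Then "Multiplying the EBV by the hematocrit (Hct) gives the red blood cell (RBC) volume", and the loss of red cells is "Total RBC volume loss = EBV x (Hct Preop – Hct Postop" (a closing bracket follows in print). Transfusion enters next: "Transfusions (mean volume per unit at HSS, 250 mL) can be taken into account by calculating the total blood loss". The last line is "Total blood loss (L) = Total RBC volume loss + (No. of Units Transfused x 0.25) / (Hct Preop – Hct Postop) / 2", and in both places a further closing bracket stands directly after the 2. No other formula for total blood loss appears.

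The postoperative value is either the postoperative hemoglobin or, in parentheses, the "lowest postoperative hemoglobin during the hospital stay prior to transfusion". Section 3 collects two unit counts: "Intra-operative transfusion requirements (units of blood" from the operating room record and "Transfusion requirement during inpatient stay (units required" from the electronic record (each item closes with a bracket). It also records the cell-saver volume in mL. The target is stated as a blood volume: "We will power the study to detect a 250mL difference in calculated intra-operative blood loss between groups".

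**The concern.** By the plan's own relation, a volume of blood V at hematocrit H contains V × H of red cells. Getting from red cells back to blood therefore means dividing by a hematocrit level. The printed line divides by a difference between two hematocrits, and that division reaches only the transfusion term. Red-cell loss stands alone outside it.

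The t-test and the regression both use this variable. Followed literally, each arm would mix untransfused patients on a red-cell scale with transfused patients on another scale, so a patient's score would depend on whether a unit was given as well as on bleeding. Two analysts who mend the bracket differently would obtain different primary results from the same data. A 250 mL difference in blood loss cannot be read off such a variable.

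**Working it through.** **Notation.** A and B are the preoperative and postoperative hematocrits, d = A − B, R = EBV × d (red-cell loss), and U is units transfused. The EBV coefficients and the 0.25 L per unit are the plan's. Body size and hematocrits are my assumptions. There is no plan figure to reproduce first: the pilot mean cannot be recomputed without the 24 cases.

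**1. Brackets.** Leaving aside the (L), the line has two opening and three closing brackets, in both copies.

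**2. Repairs.** Inserting one opening bracket at every position, or deleting any one closing bracket, gives nine valid expressions, which reduce to three formulas:

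- F1 = R + 0.25U/d/2 (six repairs)
- F2 = R + 0.25U/(d/2) (one repair)
- F3 = R + 0.25U/(A − B/2) (two repairs)

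With U = 0 each equals R (F1 and F2 are undefined if d is exactly 0). Dividing the whole sum by the difference needs brackets that are not in the line. It gives an untransfused patient R/d/2 = EBV/2 or R/(d/2) = 2 × EBV, neither of which depends on the fall in hematocrit.

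**3. Blood volume of the assumed boy (1.20 m, 22 kg).** EBV = 0.3669 × 1.2³ + 0.03219 × 22 + 0.6041 = 1.946 L.

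**4. No unit, 38% to 30%.** R = 1.946 × 0.08 = 0.156 L. Divided by a hematocrit level: 0.156/0.38 = 0.410 L (preoperative), 0.156/0.34 = 0.458 L (mean), 0.156/0.30 = 0.519 L (postoperative). The printed result is the blood loss multiplied by the chosen hematocrit, whatever the body size, so roughly a third of it.

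**5. The target on that scale.** Take untransfused losses of 671 and 421 mL for this boy, 250 mL apart, using the mean-hematocrit divisor. Solving EBV × (0.38 − B)/((0.38 + B)/2) for B gives 0.2682 and 0.3058, hence R = 218 and 144 mL, which are 73 mL apart before rounding.

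**6. One unit (litres).**

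| Hct fall | R (no unit) | F1 | F2 | F3 |
|---|---|---|---|---|
| 38% to 28% | 0.195 | 1.445 | 5.195 | 1.236 |
| 38% to 24% | 0.272 | 1.165 | 3.844 | 1.234 |
| 38% to 21% | 0.331 | 1.066 | 3.272 | 1.240 |

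At 38% to 24% the unit adds 0.25/0.14/2 = 0.89 L (F1), 0.25/0.07 = 3.57 L (F2) or 0.25/(0.38 − 0.12) = 0.96 L (F3), against a 0.25 L target.

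**7. Deeper falls.** With A fixed at 38%, the added term shrinks as B goes from 28% to 21%: 1.250 to 0.735 (F1), 5.000 to 2.941 (F2), 1.042 to 0.909 (F3). Under F1 and F2 the deeper fall scores as less bleeding. F3 does not reverse here.

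**8. Which units, and what a unit contains.** A unit given after the sample used for B has not raised B, so adding it counts the same loss twice. At 38% to 24% the mean-hematocrit form gives 0.272/0.31 = 0.88 L with no earlier unit. With one earlier unit it gives (0.2725 + 0.125)/0.31 = 1.28 L or (0.2725 + 0.175)/0.31 = 1.44 L if 50% or 70% of the 250 mL is red cells (assumed range), and (0.2725 + 0.25)/0.31 = 1.69 L if all of it is. The plan calls 250 mL the mean volume per unit and does not give its red-cell content.

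**The case against.** The strongest reply is that this is a transcription slip which the analysis would not follow. An F2 result of 5.19 L in a child with 1.946 L of blood would be noticed. For another assumed boy (1.30 m, 28 kg, 36% to 27%, EBV 2.311 L), R = 2.311 × 0.09 = 0.208 L, while 0.208/0.315 = 0.66 L, close to the pilot mean of 671.24 mL. That suggests a workable formula was used for the pilot, but one assumed child cannot prove it, and the documents do not say which formula it was. Nor is a PDF reading fault likely, since both copies agree on the stray bracket and the minus sign.

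Four stronger readings are tempting, and the documents do not support them.

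- *The added term always shrinks as the fall grows.* For F3 this needs a fixed preoperative value: 42% to 32% adds 0.25/0.26 = 0.96 L, yet the larger fall from 34% to 22% adds 0.25/0.23 = 1.09 L.
- *Transfused units are always counted twice.* The postoperative value is an unresolved choice. Double counting arises only for units given after the sample used. Intraoperative units precede every postoperative sample and belong in the sum.
- *Unit times must be collected.* Section 3 already separates intraoperative from inpatient units, which is enough if the pre-transfusion value is used.
- *The mean hematocrit is the right divisor.* The plan's relation calls for a level without saying which. Only the trailing division by 2 points to a mean.

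**Conclusion.** The formula is wrong as written and must be corrected before analysis. That rests on the text alone: the bracket does not close, the divisor is a difference, and no one-bracket repair puts an untransfused patient on a blood-loss scale. The factor of about a third for untransfused patients holds at any body size. The litre figures are illustrations for single assumed children.

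A reader might infer that the treatment comparison is biased in a known direction or by a known amount. The documents do not show this, because they give no transfusion rate. A reader might also infer that the power calculation falls with the formula. A uniform change of scale would not by itself alter power, and the pilot mean and SD may come from a different, sound formula. What is established is a mislabelled outcome and a mixture of scales within each arm if the line is followed.

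**What to change.** Print one balanced formula in both places, dividing the whole red-cell loss, including the red cells in counted units, by a hematocrit level. A provisional form is

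[EBV × (Hct Preop − Hct Postop) + red-cell volume of counted units] / [(Hct Preop + Hct Postop)/2],

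to be confirmed against the plan's cited source before analysis. With it:

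- Settle which postoperative value is used, and count only units given before that sample. If it is the postoperative pre-transfusion value, the existing split of unit counts suffices, and the text should say that loss after the first postoperative transfusion is not captured. If a later sample is used, record the time of each unit.
- State whether 250 mL is total unit volume or red-cell volume, and if it is total volume, enter the red-cell volume per unit.
- State how returned cell-saver red cells are handled. They raise the postoperative hematocrit, and neither the printed line nor the provisional form allows for them.
- Confirm which formula produced the pilot mean of 671.24 mL and SD of 233.69, and restate these and the power if it differs.

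The cost is one corrected line in two places, a few defining sentences, a check of the source and of the 24 pilot cases, and at most one field taken from the chart. Study procedures do not change.
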